10.2 Demographics and Medical/Surgical History

10.2.1 Demographics

Demographic data will be collected, including each subject's sex, age, race, and ethnicity.

10.2.2 Medical and Surgical Histories

The investigator or designee will collect the subject's medical and surgical histories, including information on the subject's concurrent medical conditions. All findings will be recorded on the medical history eCRF.

A *complete medical history* at the Screening Visit will include, but will not be limited to, the following information:

- Date of diagnosis of asthma
- Current medications
- Past medications
- History of hospitalization and intubations for asthma
- History of allergies
- History of asthma exacerbations

The subject's interval history of asthma exacerbations is to be obtained at every scheduled study visit (except Day 4); *clinically significant asthma exacerbation* is defined as a > 20% decrease in AM or PM peak flow measurements sustained for 2 days, a doubling of the inhaled corticosteroid dose, initiation of an oral corticosteroid burst for asthma or an emergency department visit/hospitalization for asthma.

A *complete surgical history* at the Screening Visit will include, but not be limited to, any history of upper or lower airway surgeries, such as sinus or laryngeal surgery. An *interval surgical history* is to be obtained at every scheduled study visit (except Day 4 and any unscheduled visits).

10.3 Physical Examination

The investigator or designee will conduct a complete physical examination at Screening and a targeted physical examination at selected time points thereafter.

Physical examination findings prior to the first dose of study drug administration will be recorded on the medical history eCRF; clinically significant findings after the first study drug dose will be recorded as AEs.

At a minimum, the *complete physical examination* should include assessments of the skin, head and neck, lungs, cardiovascular (CV) system, abdomen, thyroid, and extremities. A *targeted physical examination* will include assessment of the lungs and any new subject complaints or changes from baseline.

10.4 Vital Signs

The following vital sign measurements will be performed: systolic (SBP) and diastolic blood pressure (DBP), pulse, respiration rate, and temperature. On dosing days, vital signs will be taken pre-dose. Vital signs (except for temperature) will also be periodically monitored for a minimum of 30 minutes following the SC administration of study drug. The subject must be seated or in a semi-recumbent position in a rested, calm state for at least 3 minutes before vital signs are collected. The position selected for a subject should be the same throughout the study and documented on the vital signs eCRF.

Height will be measured without shoes at Screening.

Weight without shoes will be obtained at Screening. On dosing days, weight will be obtained before dosing. The weight at Screening will be used to calculate all study drug doses, unless there has been a weight change of $\geq 20\%$ from Screening.

10.5 Asthma Clinical Status Assessment

The investigator and/or designee will conduct an asthma clinical status assessment at specific time points, as specified in the SOE. These clinical status assessments will include:

- Pulmonary function test
- FeNO level measurement
- PRO assessment, ACQ-6

A history of *clinically significant asthma exacerbations* (defined as a $> 20\%$ decrease in AM or PM peak flow measurements sustained for 2 days, a doubling of the inhaled corticosteroid dose, initiation of an oral corticosteroid burst for asthma or an emergency department visit/hospitalization for asthma) will be obtained at each scheduled study visit (other than Day 4) and any unscheduled visits. Diary entries that meet the criteria for a clinically significant exacerbation should also be recorded in the eCRF.

10.6 Pulmonary Function Assessment

Spirometry will be performed at every visit by the investigator or qualified designee according to ATS/European Respiratory Society (ERS) guidelines [REDACTED]. Spirometry testing should be started each day between 6 AM and 12 PM; every effort should be made to conduct spirometry testing at the same time at every study visit. Spirometry should be performed before study drug or placebo administration. Subjects should refrain from strenuous exercise for a minimum of 30 minutes prior to spirometry testing and must not use short-acting bronchodilator medication within 6 hours, and long-acting bronchodilator medications within 12-24 hours (as determined by

the regular dosing interval for the specific long-acting bronchodilator medication), prior to spirometry testing. If the subject takes these medications within the prohibited timeframe, spirometry testing should be rescheduled.

The subject should rest for at least 15 minutes prior to the test. The subject should be sitting during spirometry testing; however, if the subject is unable to sit, then standing is acceptable. Spirometry testing should be completed in the same manner (ie, sitting or standing) at every study visit. Multiple forced expiratory efforts (at least 3, but no more than 8) will be performed for each spirometry session, and the 2 best efforts that meet ATS/ERS acceptability and reproducibility criteria will be recorded. The best efforts will be based on the highest FEV1. The maximum FEV1 of the 2 best efforts will be used for the analysis. Both the absolute measurement (for FEV1 and forced vital capacity [FVC]) and the percentage of predicted normal value will be recorded using appropriate reference values. The highest FVC will also be reported, regardless of the effort in which it occurred (even if the effort did not result in the highest FEV1). Nose clips may be used for spirometry; however, if nose clips are used, they should be used consistently for all spirometry.

Post-bronchodilation (BD) spirometry testing, when performed, will be assessed after the subject has induced maximal BD using a short-acting beta agonist (SABA), such as albuterol (90 µg metered dose) or salbutamol (100 µg metered dose) or equivalent, with a spacer device for a maximum of 8 total puffs [REDACTED] according to ATS/ERS guidelines (Miller 2005), a dose of 400 µg salbutamol/albuterol or lower is recommended for the reversibility test. The same number of puffs (ie, 4, 6, or 8 puffs) and post-BD maneuvers should be used each time post-BD spirometry testing is performed.

10.7 FeNO Assessment

The level of FeNO will be measured in each subject at every study visit (other than Day 4) using a standardized single-breath FeNO (American Thoracic Society; ATS, 2005) test. FeNO testing must be completed before spirometry is performed. In addition, subjects should not eat or drink within \leq 1 hour prior to FeNO measurement.

The subject should be sitting during FeNO testing; however, if the subject is unable to sit, then standing is acceptable. FeNO testing should be completed in the same manner (ie, sitting or standing) at every study visit using the same equipment. Subjects are to inhale to total lung capacity through the NIOX VERO® Airway Inflammation Monitor, then exhale for 10 seconds at 50 mL/sec (assisted by visual and auditory cues). The obtained value will be recorded and the process repeated, for a total of 2 measurements. The 2 measurements will be printed to serve as a source document.

10.8 Home Peak Flow Testing

Home peak flow testing for peak expiratory flow rate (PEFR) will be performed twice daily, in the morning upon awakening and in the evening before bedtime, using a peak flow meter. PEFR will be recorded during the Screening, Treatment, and Safety Follow-up Periods in the eDiary. PEFR measurements should be taken at least 6 hours after the last dose of SABA rescue medication. Subjects should perform 3 successive peak flow maneuvers while the subject is sitting or standing, but the subject should be in the same position at every testing. The highest of the 3 values should be captured for each time point. At each study visit, the investigator or authorized delegate will check the subject's compliance with the peak flow measurements and confirm that the subject is using the peak flow meter correctly.

10.9 Measurement of Patient-reported Outcomes

10.9.1 Asthma Daily Diary

The subject's Asthma Daily Diary (eDiary) will be provided at Screening and includes the following daily assessments: asthma symptoms; peak expiratory flow rate measurements; use of controller and rescue medication; nighttime awakening due to asthma; and asthma-related activity limitations. The eDiary will be completed each morning and evening. Triggers will alert subjects to signs of worsening of asthma, and they will be instructed to contact their investigator.

10.9.2 Asthma Control Questionnaire-6

The ACQ-6 is a patient-reported questionnaire that assesses asthma symptoms (ie, nighttime waking, symptoms on waking, activity limitation, shortness of breath, and/or wheezing) and daily rescue bronchodilator use during the past week [REDACTED] Questions are equally weighted and scored from 0 (totally controlled) to 6 (severely uncontrolled). The mean ACQ-6 score is the mean of the responses. Mean scores of ≤ 0.75 indicate well-controlled asthma, scores between 0.75 and ≤ 1.5 indicate partly controlled asthma, and a score > 1.5 indicates uncontrolled asthma [REDACTED] individual changes of at least 0.5 are considered clinically meaningful. The subject's ACQ-6 score will be assessed at every study visit prior to pulmonary function and FeNO assessments.

10.10 12-Lead Electrocardiography

The subject must be in a seated, semi-recumbent, or supine position in a rested, calm state for at least 10 minutes before ECG assessment is performed. Each 12-lead ECG should be performed prior to blood draws, dosing (if applicable), or other invasive procedures.

A single ECG will be recorded using the equipment provided by the Sponsor designee. The investigator or designated study site physician will review, sign, and date all ECGs.

[figure not shown]
Any clinically significant abnormal ECG findings will be recorded as an AE.

10.11 Clinical Laboratory Tests

10.11.1 Safety Laboratory Tests

Blood samples will be collected according to the SOE (Section 2.2), protocol Section 12, and below. All safety laboratory tests will be performed at the central laboratory. Samples will be collected pre-dose on study dosing days. Repeat laboratory testing will not be required if a test was already performed within the specified time window for collection. Samples may be analyzed for the tests outlined in this protocol and for any additional tests necessary to ensure each subject's safety. These may include, but are not limited to, investigation of unexpected results. Subjects will be in a seated, semi-recumbent, or supine position during blood collection.

During the Treatment Period, ALC must be monitored by the investigator within 7 days prior to dosing (Section 9.3.2).

10.11.2 Central Laboratory Tests

Validated assays will be used for analysis of serum samples for determination of EQ001 and treatment-emergent anti-EQ001 antibodies (anti-drug antibody [ADA]) concentrations. Collection procedures are described in the study Laboratory Manual.

10.11.2.1 Pharmacokinetics

Serum will be assayed for EQ001 concentrations using a validated assay. The PK samples will be collected at time points specified in the SOE; the PK samples should be obtained after the ECG is recorded.

10.11.2.2 Anti-Drug Antibody and Neutralizing ADA

Serum samples will be obtained for detection of ADA against EQ001 at the time points specified in the SOE, and, if required, a neutralizing ADA (NAB) assay will be performed on the same samples. Samples will be taken on Study Days 1, 29, and 57 (pre-dose), and on Study Day 85 or ET.

Short	Short	Very Long
Very Long	Very Long	Very Long
Short	Medium	Long
Short	Medium	Very Long
Short	Medium	Long
Short	Medium	Long

Term	Percentage
GMOs	~75%
Organic	~95%
Natural	~85%
Artificial	~65%
Organic	~95%
Natural	~85%
Artificial	~65%
Organic	~95%
Natural	~85%
Artificial	~65%

[REDACTED]

[REDACTED]

[REDACTED]

[REDACTED]

[REDACTED]

[REDACTED]

[REDACTED]

11 ADVERSE EVENTS

An *adverse event* (AE) is defined as any unfavorable and unintended sign (including an abnormal laboratory finding), symptom, or disease or any worsening of a pre-existing condition temporally associated with the use of a study drug, whether or not related to study drug. The AEs that occur after the first dose of EQ001 or during the study treatment and safety follow-up periods will be documented on the AE eCRF. The investigator will assess AE severity and the causality relationship of the AE to study drug. The investigator will treat the subject as medically required to ensure the subject's safety.

Laboratory values that are outside the laboratory reference range should be reported as AEs only if the investigator considered those AEs to be clinically significant.

From the time of signing the ICF through the first study drug administration, all SAEs and nonserious AEs related to protocol-mandated procedures will be recorded on the SAE/AE eCRF. All other untoward medical occurrences observed during Screening, including exacerbation or changes in the medical and surgical history, will be captured on the medical and surgical history eCRF. Details on recording and reporting AEs are provided below. All AEs will be captured through Study Day 85 or the ET Visit.

Investigators should use their clinical judgment to determine whether a subject is to be withdrawn due to an AE. In the event the subject requests to withdraw from study-related treatment or the study due to an AE, the subject should be asked to return for all remaining study visits through Study Day 85. In the event a subject is withdrawn from study, an ET Visit should be completed.

All subjects experiencing AEs, including clinically significant abnormal laboratory values, whether or not associated with use of the study drug, must be monitored until the condition (1) returns to normal, (2) returns to the subject's baseline, (3) the investigator determines the AE has reached a stable outcome and is no longer clinically significant, or (4) the subject is considered lost to follow-up.

11.1 Severity

All AEs, both serious and nonserious, will be assessed for severity using the NCI CTCAE v 5.0. The CTCAE scale includes unique clinical descriptions of AEs categorized by anatomy and/or pathophysiology. Reference the following website:

https://ctep.cancer.gov/protocolDevelopment/electronic_applications/docs/CTCAE_v5_Quick_Reference_8.5x11.pdf

Equillium AUS Pty Ltd	Clinical Study Protocol No. EQ001-19-001	Page 54 of 79
-----------------------	--	---------------

The CTCAE scale displays Grades 1 through 5 with unique clinical descriptions of severity for each AE (including abnormal laboratory values), based on this general guideline provided in the scale. For AEs not covered by CTCAE, the conventional definition of severity will be used, as follows:

- Grade 1 (mild) AE: Minor; no specific medical intervention; marginal clinical relevance.
- Grade 2 (moderate) AE: Minimal intervention; local intervention; noninvasive intervention.
- Grade 3 (severe) AE: Significant symptoms requiring hospitalization or invasive intervention.
- Grade 4 (life-threatening or disabling) AE: Complicated by acute, life-threatening complications; need for intensive care or emergent invasive procedure.
- Grade 5: Fatal AE.

11.2 Causality Assessment

The investigator or qualified subinvestigator is responsible for assessing and assigning the causality relationship of the event to study drug using clinical judgment and the following categories of relatedness:

- Related: There is at least some possibility that the AE could be related to study drug administration.
- Not related: There is a high degree of certainty that the AE is NOT related to study drug administration.

The investigator or qualified subinvestigator is also responsible for assessing and assigning the causality relationship of the event to study-related procedures (eg, invasive procedures, such as venipuncture) using clinical judgment and the following categories of relatedness:

- Related: There is at least some possibility that the AE could be related to study drug administration.
- Not related: There is a high degree of certainty that the AE is NOT related to study drug administration.

In making a causality assessment of an AE, it should be considered as to whether or not the AE is expected to occur due to the underlying disease, based on the investigator's clinical experience in managing moderate-to-severe uncontrolled asthma (Section 10.5).

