11.5 Reporting Adverse Events

11.5.1 Reporting Procedures for Nonserious Adverse Events

The investigator is responsible for ensuring that all AEs observed by the investigator or designee or reported by the subject are reported using the AE eCRF.

The investigator will assign the following AE attributes:

- AE diagnosis or syndrome(s), if known (if not known, signs or symptoms)
- Dates of onset and resolution (if resolved)

Equillium AUS Pty Ltd	Clinical Study Protocol No. EQ001-19-001	Page 56 of 79
-----------------------	--	---------------

- Severity
- Causality relationship to study drug or study-related procedures
- Action taken
- Outcome

Follow-up of nonserious AEs will continue through the last day on the study and/or until a definitive outcome (eg, resolved, resolved with sequelae, lost to follow-up) is achieved.

When a subject is withdrawn from the study because of a nonserious AE, the Sponsor and/or designee must be notified by email or phone within 48 hours.

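### Protocol 11.2 defines relatedness to study procedures in study-drug wording, so the procedure categories contradict the assessment they belong to

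*Protocol*

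**What the plan says.** Protocol 11.2 sets two tasks. The first is to judge whether an event is related to study drug. The second is to assign the "causality relationship of the event to study-related procedures (eg, invasive procedures, such as venipuncture) using clinical judgment and the following categories of relatedness". Each task is followed by a 'Related' and a 'Not related' definition. The two pairs are identical. Under the procedure task, 'Related' means "There is at least some possibility that the AE could be related to study drug administration" and 'Not related' means "There is a high degree of certainty that the AE is NOT related to study drug administration". Neither definition in the second pair mentions a procedure.

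The procedure judgement is used elsewhere in the protocol:

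- Section 11.5.1 lists among the attributes assigned to an AE: "Causality relationship to study drug or study-related procedures". Section 11.5.2 requires the same assessment for SAEs.
- Section 11 uses relation to procedures to decide what is recorded as an AE before dosing. "From the time of signing the ICF through the first study drug administration, all SAEs and nonserious AEs related to protocol-mandated procedures" go on the SAE/AE eCRF. The history form takes the remainder: "All other untoward medical occurrences observed during Screening, including exacerbation or changes in the medical and surgical history, will be captured".

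In the SAP, Section 10.3 summarizes relatedness to study drug. It places AEs that precede treatment in listings only. The visible text has no summary by relatedness to procedures.

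**The concern.** A protocol asks two causality questions so that harm from being in the study can be told apart from harm from the drug. Here the second question is asked correctly and then answered on the first question's scale. The instruction and its categories conflict, and sites may resolve the conflict differently.

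The distinction has some content in this trial. Safety and tolerability is the primary objective, and the subjects have uncontrolled asthma. Protocol 10.6 has them withhold short-acting bronchodilators for 6 hours and long-acting ones for 12 to 24 hours before spirometry, and then make 3 to 8 forced efforts. An event provoked by that, or by a blood draw, is what the procedure question is there to identify. What is at stake is whether such events carry the correct label and, before first dose, which form they are entered on.

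**Working it through.** There is no figure in the plan to reproduce and no formula to apply. The check compares the intended rating with the literal one.

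**Inputs.** The two tasks and two pairs of definitions come from Protocol 11.2, the pre-dose recording rule from Protocol 11, and the use of relatedness in analysis from SAP 10.3.

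**Step 1: the four possible kinds of event.** An event either may or may not be due to drug, and either may or may not be due to a procedure. The intended procedure rating follows the sentence that introduces the categories. The literal rating follows the printed definitions.

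| Kind of event | Drug rating | Procedure rating, intended | Procedure rating, literal |
|---|---|---|---|
| Procedure only (eg, venipuncture bruise) | Not related | Related | Not related |
| Possibly drug, no procedure involved | Related | Not related | Related |
| Procedure involved and drug not excluded (eg, an injection-site event) | Related | Related | Related |
| Neither | Not related | Not related | Not related |

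The literal rating is wrong in two of the four kinds, one in each direction. These are the two kinds where the drug and procedure answers should differ. The drug column is right throughout, because the first pair of definitions is right. The table counts kinds of event; it says nothing about how often each occurs.

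**Step 2: before first dose.** No study drug has been given, so only the first and fourth rows can arise. On the printed definitions both are 'Not related' to procedures. If a site used that rating to apply the Section 11 rule, a nonserious event caused by a screening procedure would fail the test for the AE form and go to the medical and surgical history form. Section 11 does not cite the 11.2 categories, so this step depends on how sites work. SAEs do not turn on it: Protocol 11.4 has all SAEs reported within 24 hours whatever their cause.

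**Step 3: effect on the analysis.**

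- DLTs, in the Protocol Synopsis and SAP 10.3, are defined by relation to study drug.
- Treatment-related TEAEs and TESAEs in SAP 10.3 also use relation to study drug.
- AEs before treatment are listed and not tabulated. A misfiled screening event would leave the AE listing and appear in the medical history table and listing of SAP 7.5.
- No visible SAP table uses the procedure rating.

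**The case against.** The strongest reply is that this is a copying slip with an obvious meaning. The introducing sentence names venipuncture and asks for clinical judgement, and Sections 11.5.1 and 11.5.2 repeat that relation to procedures is to be assessed. An investigator told to judge venipuncture is unlikely to call a venipuncture bruise unrelated to it. This stands as an argument about likely practice. It does not make the printed categories correct, and no other definition of procedure relatedness is visible.

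Three stronger inferences are tempting, and the documents do not support them.

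- *A reader might infer that the pre-dose rule captures no nonserious AE at all.* Section 11 states its own test in plain words, relation to protocol-mandated procedures, and does not refer to the 11.2 categories. An investigator can apply it directly. Any event that was misdirected would still be recorded, on the history form.
- *A reader might infer that every procedure-caused event becomes 'Not related'.* The third row of the table shows otherwise: where a drug role cannot be excluded, the literal rating is 'Related'. After Day 1, with repeated dosing, high certainty that the drug played no part is not automatic.
- *A reader might infer that procedure harm can no longer be separated from drug harm.* The drug rating is correctly defined, so an event due only to a procedure is still rated not drug-related. What may be lost is its positive attribution to the procedure. The two ratings do coincide on the printed definitions, but Section 11.5.1 gives the attribute in one line, and the documents do not show how the eCRF words or separates the fields.

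**Conclusion.** The procedure-relatedness categories in Protocol 11.2 are wrong as written and contradict their own introduction. Read literally, they misclassify events caused only by a procedure, and they label as procedure-related those events that may be due to drug but to no procedure. Misfiling of nonserious screening events as medical history is a conditional consequence: it needs sites to carry the printed categories into the Section 11 rule.

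The point is minor. Drug relatedness, DLTs, SAE reporting and the SAP's TEAE tables are unaffected. That assumes investigators rate drug relatedness from the first, correct pair of definitions. No count of affected events can be given: it would depend on site practice and on the eCRF wording, and the documents show neither. The point is an internal inconsistency and not a design choice.

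**What to change.** In the second pair of definitions in Protocol 11.2, replace *study drug administration* with *a study-related procedure*, in both 'Related' and 'Not related'. Leave the first pair alone. Then check that the AE/SAE eCRF fields and any completion help use the corrected wording.

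The cost is two lines of text and one eCRF check. No data item, analysis or SAP change is needed, because Section 11.5.1 already has causality to procedures assigned. Protocol 14.2 requires ethics committee approval of amendments, so the correction is best carried with the next one.
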